10.1.4.1 Preparatory Barriers

- Patients Expectations for Their Role in a SDM Encounter

Control Preferences Scale (baseline patient survey): The Control Preferences Scale (CPS) is validated survey instrument that was developed to measure patient's preferred and/or perceived roles in their health-care decision-making; it consists of a single item. The roles range from the individual making the treatment decision, through the individual making the decision jointly with the physician, to the physician making the decision.⁷⁷

Preparation for Decision Making Scale (follow-up patient survey): The ten-item Preparation for Decision Making (PrepDM) scale was developed to evaluate decision processes relating to the preparation of patients for decision making and dialoguing with their practitioners.⁷⁸ It has been demonstrated to be reliable and valid, and discriminates based on perceived usefulness of decision support tools.

- Patients' Knowledge about the Decision Faced:

"How informed do you feel?" (baseline patient survey): We will ask how informed patients feel about the surgical options for breast cancer before their consultation with the surgeon.

SURE Decisional Conflict Scale (follow-up patient survey): The 4-item SURE (Sure of myself; Understand information; Risk-benefit ratio; Encouragement) screening test was developed to help health professionals identify patients with clinically significant decisional conflict as quickly as possible.⁸¹

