We will first perform analyses to test and quantify the extent to which the effect of the decision aid intervention on patient engagement endpoints is mediated through the mitigation of candidate preparatory and interactional barriers. We will quantify the indirect effect relative to the total effect of the decision aid in joint linear structural equation models (SEM) for the endpoint and the candidate mediators, including random surgeon effects and random region effects for each of the mediator and endpoint parts of the models. Each of the preparatory and interactional Barriers will be represented by a continuous latent construct in the SEM, with 3 and 5 observed items for Preparatory and Interactional Barriers, respectively. Binary or count variables will be modeled via latent continuous construct in the SEM. Structural equation models will be specified, estimated and tested using Mplus v7.3.⁹⁷ The use of unidimensional latent constructs increases power and reduces the number of tests, relative to testing each observed item separately. Standardized coefficient estimates from the SEM, representing total, direct, and indirect effects, will allow for the determination of whether the mechanism by which the decision aid leads to increased patient engagement is through the mitigation of preparatory and/or interactional barriers (see Figure 7 for simplified example). For example, if coefficient X is important but Y is not, we can conclude that although the decision aid leads to statistically significant changes in interactional barriers, this is not the mechanism through which the decision aid increases patient engagement. Alternatively, if only coefficient Y is important, we can conclude that although the interactional factors represent a significant barrier to patient engagement, the decision aid does not significantly impact the barrier.

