Finally, if we find significant indirect effects (represented in the figure by the dashed line leading from the decision aid to engagement that runs through interactional barriers), we can conclude that receipt of the decision aid leads to a change in the interactional barrier, which leads to improved patient engagement. Statistically, coefficients X and Y will be tested together, with the null hypothesis being that the product $XY=0$. If either latent construct for preparatory or interactional Barriers is significant, then each individual observed item will be tested, post hoc, as candidate barriers. Candidate barriers for the next models will be barriers for which the indirect effect is significant and/or barriers associated with lower levels of engagement (i.e. coefficient Y). Those barriers associated with lower level of engagement will be considered persistent and prioritized for inclusion in the qualitative interviews (Aim 3).

Persistent Barriers Experienced by Socioeconomically Disadvantaged Patients

We will estimate logistic and Poisson regression models with socioeconomic deprivation as the explanatory variable, and each candidate persistent barrier as described above as the outcomes, in order to assess the extent to which socioeconomic disadvantage is associated with persistent barriers to engagement. As with Aim 1, models will include surgeon and clinic random effects to account for patient clustering. Findings will guide the sampling strategy for patient interviews (Aim 3) and will be incorporated into the interview content.

[figure not shown]

Figure 7. Schematic depicting the mediating role of preparatory and interactional barriers on engagement. The dashed lines represent the test for the overall effect of whether the decision aid improves engagement through that pathway.

*Effect of decision aid on barriers; +Effect of barriers on patient engagement.

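### For the audio-coded participation endpoint, mediator scales answered after the consult cannot support the causal barrier and mediation conclusions in section 12.1.1; only an association can be claimed

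*Combined protocol and SAP*

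**What the plan says.** Co-Primary Objective #2 (section 12.1.1) fits structural equation models in which preparatory and interactional barriers are continuous latent constructs, "with 3 and 5 observed items for Preparatory and Interactional Barriers, respectively". In Figure 7, X is the path from the decision aid to the barrier and Y the path from the barrier to engagement. Section 12.1.2 confirms that the endpoints are PEPPI-5 and the active participation count.

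The plan fixes three readings or rules in advance:

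- If only Y matters, the conclusion is that "although the interactional factors represent a significant barrier to patient engagement, the decision aid does not significantly impact the barrier".
- If the indirect effect (XY) is significant, "we can conclude that receipt of the decision aid leads to a change in the interactional barrier, which leads to improved patient engagement".
- "If either latent construct for preparatory or interactional Barriers is significant, then each individual observed item will be tested, post hoc, as candidate barriers". Then, "Candidate barriers for the next models will be barriers for which the indirect effect is significant and/or barriers associated with lower levels of engagement". Barriers tied to lower engagement are called persistent and given priority in the Aim 3 interviews.

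None of these carries a condition on when the barrier was measured relative to the endpoint.

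**The concern.** A mediator has to precede the outcome it is said to affect. Active Patient Participation happens during the consult, whereas PrepDM, SURE and HCCQ are answered afterwards. An active consult that leaves the patient surer of her choice, or warmer towards her surgeon, gives the same Y as a barrier that holds participation back. The data cannot separate the two, yet the plan commits to one of them.

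What is at stake is a conclusion under a co-primary objective, plus the choice of barriers that go forward to the socioeconomic-disadvantage models and the interviews. A smaller issue is the Practitioner Orientation Scale. It is one score per surgeon, taken before patient enrolment, so the aid cannot change it and a null X for it says nothing about the aid.

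**Working it through.** **1. Item count and timing**

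| Construct | Measure | When taken |
|---|---|---|
| Preparatory (10.1.4.1) | Control Preferences Scale | before consult |
| | How informed do you feel | before consult: "We will ask how informed patients feel about the surgical options for breast cancer before their consultation with the surgeon" |
| | PrepDM | follow-up survey |
| | SURE | follow-up survey |
| Interactional (10.1.4.2) | Surgeon facilitative behaviours | recording |
| | Surgeon recommendation | recording |
| | Family member presence | recording |
| | HCCQ | follow-up survey |
| | Practitioner Orientation Scale | surgeon survey, before patient enrolment (7.2.1) |

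Four preparatory measures are listed and three are used. There are four possible sets of three. All four contain at least one follow-up scale, and two contain both. Table 10.1.5 places How informed after the consult, but 10.1.4.1 and Appendices I–II place it before. On the table's timing every set would contain at least two.

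Five interactional measures are listed and five are used, so HCCQ and the surgeon scale are both in on a plain count. This is not certain: HCCQ is said to assess both autonomy and trust. If it counts as two items, one of the six possible five-item sets omits the surgeon scale.

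**2. Order**

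Active Patient Participation is coded from the recording (10.1.1), which is T1. The follow-up survey (T2) is sent within 24 hours after the consult (11.3.1). PEPPI-5 is on that same T2 survey, so its order relative to the follow-up scales is undetermined.

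**3. The plan's own power figure**

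Take power = [Φ(√(n·R²/(1−R²)) − 2.241)]², where R² = 2% × k·r/(1+(k−1)r), k is the number of items, r = 0.60 and 2.241 is the two-sided 0.025 critical value.

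- k = 3: reliability 1.8/2.2 = 0.818 and R² = 1.636%. At n = 533, √(533 × 0.016635) = 2.978 and Φ(0.737)² = 0.59. At n = 583 it is 0.65. The plan states 60% and 65%, so this reproduces. (The reliability expression printed in 12.1.2 evaluates to 0.733, not the 0.82 used. That is a separate matter.)
- k = 2: reliability 1.2/1.6 = 0.75 and R² = 1.5%. Power is 0.53 at n = 533 and 0.59 at n = 583.

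**4. How often a barrier with no causal role would be flagged**

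Assume no mediation: the aid raises participation y by d SD, and a follow-up item equals ρ·y + √(1−ρ²)·base. The construct is the mean of three items with base correlation 0.60, n = 533, two-sided α = 0.025, no clustering. The values of ρ and d are assumptions; the documents give neither.

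With one follow-up item and ρ = 0.2:

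- Variance of the mean = [3 + 2(0.6 + 2 × 0.6 × 0.980)]/9 = 0.728.
- Correlation with y given arm = (0.2/3)/√0.728 = 0.078.
- z = 0.078/√(1−0.078²) × √533 = 1.81, so P(Y significant) = Φ(1.81−2.24) = 0.33.

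The same steps give 0.09 at ρ = 0.1, 0.69 at 0.3 and 0.99 at 0.5. Multiplying by P(X not significant) gives the Y-only rate. Simulation agrees: about 9% at ρ = 0.1, and 32–33%, 65–67% and 86–95% at ρ = 0.2, 0.3 and 0.5. Across runs this is about 30–95%.

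**5. False mediation (X and Y both significant)**

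Two precisions for the arm contrast are used: 2/√533 = 0.087, as the mediation power calculation implies, and 0.50/(2.241+0.842) = 0.162, implied by the stepped-wedge detectable effect of 0.50 SD at 80% power. Simulated rates at ρ = 0.2 / 0.3 / 0.5:

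| Follow-up items | d | SE 0.087 | SE 0.162 |
|---|---|---|---|
| one | 0.3 | 1.0 / 2.6 / 5.7% | 0.9 / 1.7 / 3.3% |
| one | 0.5 | 1.4 / 4.3 / 13.8% | 0.9 / 2.6 / 4.7% |
| two | 0.3 | 5.1 / 7.9 / 18.5% | 2.5 / 3.8 / 7.2% |
| two | 0.5 | 8.4 / 18.4 / 50.6% | 4.1 / 7.1 / 16.3% |

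**6. The gate to item-level tests**

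An item can be flagged no more often than the gate opens. With one follow-up item at SE 0.162, the gate opens in about 1–5% of trials if a significant construct means XY, and about 33–99% if it means Y. Section 12.1.1 does not say which.

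**7. The surgeon scale**

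With four items that respond to the aid and one fixed, uncorrelated item, the squared standardised effect is (4/5)²/(12.2/25) = 1.311. With five responding items it is 1/(17/25) = 1.471, and with four alone 1/(11.2/16) = 1.429. The ratios are 0.89 and 0.92, so a path X R² of 2% becomes about 1.8%.

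**The case against.** **The formal test is XY = 0 and is barely disturbed.** This stands for one follow-up item at stepped-wedge precision (about 1–5% against a nominal 2.5%), but not for two items. It leaves the Y-only reading untouched. That reading is introduced as an example, but it is worded as a conclusion.

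**The Y-only rate is mostly power to detect an assumed correlation.** True. Nothing in the documents supports ρ of 0.2–0.5, and at 0.1 the rate is about 9%.

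**The illustration is not the planned model.** It uses an item mean without clustering. A one-factor model fitted to data from the same mechanism failed the chi-square fit test in 300 of 300 trials in every cell, so the reverse path could show as misfit. That is fair, but the plan states no fit criterion and no action on misfit.

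**The gate probably means XY.** The gate sentence follows the XY = 0 null, and section 12.1.2 opens the disadvantage step with mediating barriers having been detected. Both favour that reading. The later and/or rule for candidate barriers does not, so a statement is still needed.

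**A reader might infer that mediation is ruled out, or that the disadvantage results are biased.** Neither follows. HCCQ and PrepDM ask the patient to look back, so they may reflect conditions before or during the consult. The disadvantage models regress the barrier on deprivation without the endpoint, so only the selection of barriers is affected.

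**Rebuilding the constructs without follow-up scales costs power.** It does, and two indicators identify a latent variable weakly. That argues for a sensitivity model, not a replacement.

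**Conclusion.** The concern holds for Active Patient Participation: Y or XY results that rest on PrepDM, SURE or HCCQ show association and do not support the causal wording in 12.1.1. At least one such scale is in the preparatory construct under any choice of three from the four listed measures.

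The main exposure is the Y-only barrier reading and the choice of barriers that follows from it. The rates of about 9% (ρ = 0.1) and about 30–95% (ρ = 0.2–0.5) are illustrative. They assume no mediation, one follow-up item, an item mean, no clustering and no fit check. False mediation is a secondary risk that matters mainly if two follow-up scales are used.

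It would go too far to say that the order is reversed for PEPPI-5, where it is only undetermined. The surgeon scale and the table 10.1.5 entry are minor corrections.

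**What to change.** Keep the planned structural equation model and its power basis, and add the following to 12.1.1:

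- Name the three preparatory and five interactional items and give the timing of each.
- For Active Patient Participation, state that Y and XY results resting on PrepDM, SURE or HCCQ will be reported as association, and that the causal conclusions will not be drawn from them. Label barriers carried forward on that basis the same way.
- Add a sensitivity model for this endpoint using only pre-consult and audio-coded measures. State its lower power (about 53% with two preparatory items against the stated 60%, at r = 0.60), and that direction is still not established for surgeon behaviour coded from the same recording.
- If the Practitioner Orientation Scale is among the five items, use it as a surgeon-level covariate or moderator.
- State that the item-level gate means a significant XY, in line with 12.1.2, or say otherwise.
- Correct table 10.1.5 so that How informed do you feel is before the consult.

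The cost is a short amendment to the analysis text and one extra model. No new data, measures or patients are needed, and the primary mediation power statement is unchanged, apart from a small gain on path X if the surgeon scale is removed.

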12.1.2 Sample Size and Power Calculations

Co-Primary Objective #1: Based on current patient enrollment, we estimate a sample size of 563 patients. This has been reduced from our original estimate of 1,050 patients. We assume 23 surgeons will participate. Aim 1 has two primary endpoints: PEPI-5 self-efficacy and Active Patient Participation Behaviors (count). We desire a family-wise two-sided Type I error rate of $\alpha=0.05$; under a Bonferroni correction, tests will be conducted with nominal of $\alpha=0.05/2 = 0.025$.

Using the revised analysis model and updated accrual projections, we estimated Fisher's information for the regression parameters when the study will have complete data; inverting that information we obtained an estimate of the standard error for the intervention effect parameter, thereby computing minimally detectable Cohen's-*D* effect size for each primary endpoint at 80% and at 90% power. As a sensitivity analysis, we considered varying estimates of ICCs to ensure robust findings.

Self-Efficacy: Assuming PEPI-5 has a standard deviation (SD) of 4.3 and both within-surgeon and within-site-between surgeon ICC of 0.07, we will have 80% power to detect effects as small as $0.55*4.3=2.4$ and 90% power to detect effects as small as $0.63*4.3=2.7$ on a scale of 5-25. We consider a difference of 2 points to be clinically meaningful.

Active Patient Participation Behaviors: Assuming the active patient participation behavior count has a standard deviation of 23.1 and a within-surgeon ICC of 0.01 and within-site-between surgeon ICC of 0.0001, we have 80% power to detect a difference of $0.50*23.1=11.6$ and 90% power to detect a difference as small as $0.57*23.1=13.2$ on a 0-150 scale. We consider a difference of 10 to be clinically meaningful.

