Co-Primary Objective #2: Mackinnon *et al.* have shown that one of the most accurate tests for mediation or indirect effect is the “asymmetric distribution of products” test¹⁰⁰ and have provided extensive simulation studies for estimating power for a variety of mediation tests.^{101,102} PowMedR software¹⁰³ was developed based on that work, which we exploit here. We assume a sample size of 563 and then deduct 23 df for surgeon effects and 7 df for number of waves; we estimate an effective sample size of 533. In addition, because we are testing two mediators, we set $\alpha=0.05/2 = 0.025$ for these two tests. Suppose we have small mediation effects with $R^2=2\%$ for the effect of the intervention on the *latent* barrier mediator (Figure 7) and for the effect of the latent mediator on PEPPi-5 score or on active patient participation behavior count. Suppose additionally that the three observed items have correlation of at least $r=0.60$. Then, the average of those three items will have reliability of $\lambda = \{r + (1/3)(1 - r)\}$, yielding net R^2 values between the intervention and the *observed* mediator and between the observed mediator and PEPPi-5 score or active patient participation behavior count of $\lambda R^2=0.82*.02=1.6\%$. Using the PowMedR software, we will have 60% power to detect mediation with small effect size and >99% power to detect mediation with medium effect size $\lambda R^2=0.82*.15=12.3\%$. Power will be higher with five items.

We will extend the period of enrollment for sites that are still recruiting within the stepped wedge design as of 8/30/2021. The extended recruitment beyond Wave 7 will continue for six sites until 12/31/2021 (see Section 12.1.3). While these additional patients will not contribute to the first co-primary objective, they will be included in the analysis for this 2nd co-primary objective; all of these additional patients will be exposed to the study intervention. We anticipate, at a minimum, that there will be 50 such patients exposed to the intervention across these six sites. We re-estimated power assuming such an increase, which leads to an increase in the power for detecting small effects from 60% to 65%.

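### Section 12.1.1 reads a non-important barrier-to-engagement path as showing that the barrier is not the mechanism; at the plan's own small effect this is wrong in about 16 to 18% of trials.

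*Combined protocol and SAP*

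**What the plan says.** Section 12.1.1 (Co-Primary Objective #2) fits structural equation models with X as the effect of the decision aid on a barrier and Y as the effect of the barrier on engagement. It then illustrates how the coefficients will be read. In the first case, "if coefficient X is important but Y is not, we can conclude that" the aid changes the interactional barrier, but "this is not the mechanism through which the decision aid increases patient engagement". In the second case only Y is important, and the conclusion drawn is that the barrier matters for engagement while "the decision aid does not significantly impact the barrier".

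The formal test is of the null hypothesis that the product XY is zero. The section promises to quantify the indirect effect relative to the total effect, so estimates will exist. The two readings above do not use them, and the section sets no equivalence margin, interval criterion or inconclusive category.

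Barriers go forward to the disadvantage models if their indirect effect is significant and/or they are associated with lower engagement (Y). Those with a Y association are prioritised for the qualitative interviews.

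Section 12.1.2 gives the precision: alpha 0.025 for each of two mediators, an effective sample size of 533, and "we will have 60% power to detect mediation with small effect size". Power is above 99% for a medium effect, and the small-effect figure rises to 65% with 50 patients recruited beyond Wave 7.

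**The concern.** A path that fails to reach significance may be absent, or it may be present and missed. The first reading allows only the former. With 60 to 65% power at the effect the plan itself calls small, the latter is a live possibility.

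Objective 2 is co-primary and exists to say which barriers the aid works through. A missed Y has two effects: it produces the flat statement, and it removes the barrier's route into the disadvantage models and the prioritised interviews, because neither Y nor the product is then significant. A working pathway could be reported as ruled out when it was only not detected.

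**Working it through.** **Inputs, all from Section 12.1.2 unless marked as assumptions**
- Effective n = 563 − 23 − 7 = 533. With the extension, 533 + 50 = 583 (assumption: each added patient counts in full).
- Small effect per path, net of measurement error: R² = 0.82 × 0.02 = 0.0164. Medium: 0.82 × 0.15 = 0.123.
- Alpha = 0.025 per mediator, taken as two-sided, critical value 2.241. Two-sidedness is stated for Objective 1 ("We desire a family-wise two-sided Type I error rate of" 0.05) and for the disadvantage tests. For the mediation tests it is an assumption.
- Assumptions: *important* means statistically significant at this alpha, which the neighbouring wording supports; the two path tests are independent; mediation is declared when both paths are significant.

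**Step 1: power per path.** With ncp = √(R²/(1−R²)) × √(n−2), power = Φ(ncp − 2.241).
- n = 533: √(0.0164/0.9836) × √531 = 0.1291 × 23.04 = 2.98; Φ(0.73) = 0.769.
- n = 583: 0.1291 × √581 = 3.11; Φ(0.87) = 0.808.

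**Step 2: reproduce the plan's figures.** Mediation power is the product of the two path powers.
- n = 533: 0.769² = 59.1%, against 60% stated.
- n = 583: 0.808² = 65.3%, against 65% stated.
- Medium effect, n = 533: ncp = 8.63, power above 99.9%, against above 99% stated.

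Other methods come close: 57.3% with R² rounded to 0.016, and 55.7% with a simulated distribution-of-product interval. The reliability formula printed in Section 12.1.2 gives 0.60 + 0.40/3 = 0.73, not 0.82. The value 0.82 equals 3r/(1+2r) = 1.8/2.2, and the stated power matches 0.82, so 0.82 is used here.

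**Step 3: split the outcomes when a small effect is real on both paths, for one barrier**

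| Outcome | n = 533 | n = 583 |
|---|---|---|
| Both paths significant | 0.769² = 59% | 0.808² = 65% |
| X only (flat negative statement) | 0.769 × 0.231 = 18% | 0.808 × 0.192 = 16% |
| Y only (softer statement) | 18% | 16% |
| Neither | 0.231² = 5% | 0.192² = 4% |
| Mediation missed, total | 41% | 35% |

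Given that X is significant, the flat statement is wrong with probability 0.231, or 23% (19% at n = 583).

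**Step 4: medium effect.** Each path is detected almost surely, so both kinds of wrong negative have probability near zero.

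**The case against.** The strongest defence has four parts. The two readings are introduced as an example, with a simplified figure. The plan commits to estimating total, direct and indirect effects. Section 12.1.2 openly discloses the modest power at small effects. And the downstream rules limit the damage: a barrier in the Y-only case is retained and prioritised, while Section 12.2.1 adds inductive coding for unrecognised barriers and ranks targets by the proportion of patients affected and by perceived impact, not by the mediation verdict.

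Most of this stands, and it narrows the point. It does not remove it. The example is the only interpretive guidance given, it says what may be concluded, and the promised estimates play no part in that conclusion. A missed Y is also not rescued by the carry-forward rule.

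Three stronger readings are tempting and not supported.
- *A wrong statement of this kind is likely.* The flat statement arises only in the X-only case, at 16 to 18%. Adding the Y-only case gives about 31 to 36%, but that wording reports that the aid does not significantly affect the barrier, which is not a claim of no effect.
- *With two barriers, error is the norm.* At least one of two independent, real, small mediators is missed 1 − 0.60² = 64% of the time (1 − 0.65² = 58% with the extension). That counts all missed mediation, not the flat statement.
- *Path X is far less precise than assumed.* If X had the precision implied by Objective 1's detectable effects of 0.50 to 0.55 SD (standard error 0.16 to 0.18 SD, with 1:1 exposure), Y-only would occur in 57 to 60% of trials. The documents do not say that this precision applies to the mediation model. Under that assumption the flat statement would also become rarer, at 5 to 6%.

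**Conclusion.** The point holds as a fault of inference in one stated reading. A non-important Y is turned into a positive conclusion of no mediation, with no criterion to support it. The size is moderate and confined to small effects: mediation missed in about 41% of trials and the flat statement wrongly made in about 18%, falling to 35% and 16% with the extension, and near zero at the medium effect. These figures rest on the plan's own inputs together with two-sided alpha, independent path tests, joint significance, and *important* read as significant. The practical harm is mainly that a missed Y labels a real pathway as ruled out and can drop the barrier from later steps. The documents do not support saying that a wrong conclusion is more likely than not, or that the Y-only reading loses barriers.

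**What to change.** In Section 12.1.1, replace the first conclusion with: *mediation through this barrier was not shown*. Replace the second with: *an effect of the aid on this barrier was not shown*. For each construct, report the 97.5% interval (matching alpha 0.025) for the indirect effect and for X and Y. State that any claim that a pathway is negligible will rest on that interval, never on non-significance.

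I would not write in a fixed margin. The obvious candidate, ±0.02 (√0.02 × √0.02), contains the plan's own net small indirect effect (√0.0164 × √0.0164 = 0.0164). Simulation at n = 533 with Y = 0 puts the interval inside that range only about 44 to 59% of the time at X = 0.141, depending on the interval method, and essentially never at X = 0.30 or above.

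The cost is SAP wording and a few intervals per construct, with no new data. The downside is that some pathways will be reported as inconclusive, which is an accurate account of what this sample size can show.
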